## 6. TRIAL POPULATION

The trial will include 184 Liver transplant recipients at up to 21 sites in the U.S.

### 6.1. Donor Eligibility Criteria

#### 6.1.1. Donor Inclusion Criteria

Donor liver meets at least one of the following:

- Donor age  $\geq$  40 years old; or
- Expected total cross clamp time  $\geq$  6 hours; or
- Donor after circulatory death (DCD) with age  $\leq$  55 years old; or
- Steatotic liver  $> 0\%$  and  $\leq 40\%$  macrosteatosis at time of retrieval (based on retrieval biopsy readout only if the donor liver was clinically suspected to be fatty by the retrieval surgeon at time of liver retrieval).

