Donor Liver Eligibility Criteria	
Inclusion
 
Donor meets at least one of the following:
 
 
• Donor age <math>\geq</math> 40 years old; or
 
• Expected total cross clamp time <math>\geq</math> 6 hours; or
 
• Donor after circulatory death (DCD) with age <math>\leq</math> 55 years old; or
 
• Steatotic liver <math>> 0\%</math> and <math>\leq 40\%</math> macrosteatosis at time of retrieval (based on retrieval biopsy readout (only if the donor liver was clinically suspected to be fatty by the retrieval surgeon at time of liver retrieval)).
 
 
Exclusion
 
Donor livers will be excluded if they meet any of the following criteria:
 
 
• Living donors
 
• Liver intended for split transplants
 
• Positive serology (HIV, Hepatitis B surface antigen & Hepatitis C)
 
• Presence of moderate or severe traumatic liver injury, or anatomical liver abnormalities that would compromise ex-vivo perfusion of the donor liver (i.e., accessory blood vessels or other abnormal anatomy that require surgical repair) and livers with active bleeding (e.g., hematomas)
 
• Donor livers with macrosteatosis of <math>> 40\%</math> based on retrieval biopsy readout.
 

Recipient Eligibility Criteria	
Inclusion
 
Recipients are required to meet all the following criteria on the day of transplant:
 
 
• Registered primary Liver transplant candidate, male or female
 
• Age <math>\geq 18</math> years old
 
• Signed: (1) written informed consent document and (2) authorization to use and disclose protected health information.
 
 
Exclusion
 
Recipients will be excluded if they meet any of the following criteria on the day of transplant:
 
 
• Acute, fulminant liver failure
 
• Prior solid organ or bone marrow transplant
 
• Chronic use of hemodialysis or diagnosis of chronic renal failure, defined as chronic serum creatinine of <math>> 3</math> mg/dl for <math>> 2</math> weeks and/or requiring hemodialysis
 
• Multi-organ transplant
 
• Ventilator dependent
 
• Dependent on <math>> 1</math> IV inotrope to maintain hemodynamics.
 

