## 4. TRIAL OBJECTIVES

To evaluate the effectiveness of the OCS Liver System to preserve and assess donor livers having one or more of the following characteristics:

- Donor age  $\geq$  40 years old; or
- Expected cross clamp time  $\geq$  6 hours; or
- Donor after circulatory death (DCD) with age  $\leq$  55 years old; or
- Steatotic liver  $> 0\%$  and  $\leq 40\%$  macrosteatosis at time of retrieval (on pre-retrieval histology).

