#### 6.1.2. Donor Exclusion Criteria

Donor livers will be excluded if they meet any of the following criteria:

- Living donors
- Liver intended for split transplants
- Positive serology (HIV, Hepatitis B surface antigen & Hepatitis C)
- Presence of moderate or severe traumatic liver injury, or anatomical liver abnormalities that would compromise ex- vivo preservation of the donor liver (i.e., accessory blood vessels or other abnormal anatomy that require surgical repair) and livers with active bleeding (e.g., hematomas)

- Donor livers with macrosteatosis of > 40% based on retrieval biopsy readout.

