### **10.2. Analysis Populations**

#### **10.2.1. Per Protocol Population**

The Per Protocol (PP) Population will consist of all subjects who are transplanted and have no major protocol violations and for whom the donor liver received the complete preservation procedure. The major protocol violations that will exclude a subject from this population are the following:

- Ineligible for the study according to the recipient inclusion and exclusion criteria
- Ineligible for the study according to the donor organ inclusion and exclusion criteria
- Failure to complete adequate post-transplant assessments to support the primary, secondary or safety endpoints
- Other major protocol violations.

The primary analysis of effectiveness and of secondary and other endpoints will be based on the PP Population.

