### **10.3.4. Primary Effectiveness Endpoint**

The primary effectiveness endpoint for this study is the incidence of Early Liver Allograft Dysfunction (EAD) or primary non-function, defined as presentation of one or more of the following criteria:

- AST level > 2000 IU/ml within the first 7 postoperative days;
- Bilirubin  $\geq$  10 mg/dl on postoperative day 7;
- INR  $\geq$  1.6 on postoperative day 7; or
- Primary non-functioning graft within the first 7 days.

This endpoint will be analyzed using the Per Protocol and mITT Populations. The Per Protocol analysis will be considered the primary analysis.

Subgroup analyses of the primary effectiveness endpoint will be performed for the following subgroups of patients:

- DCD (donation after circulatory death) patients
- Fatty liver patients
- Donor Age
- Recipient with MELD  $>$  30.

No data imputation or statistical tests will be performed for these subgroup analyses.

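### Does the 55-year limit on DCD donors need to change because, as written, it excludes nobody?

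*Combined protocol and SAP*

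**What the plan says.** Section 6.1.1 opens with "Donor liver meets at least one of the following" and lists four items joined by *or*:

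- donor age of at least 40 years;
- expected total cross-clamp time of at least 6 hours;
- "Donor after circulatory death (DCD) with age" no more than 55 years;
- macrosteatosis above 0% and up to 40%.

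The synopsis uses the same rule ("Donor meets at least one of the following"). Section 4 states the objective for "donor livers having one or more of the following characteristics" and gives the same items.

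The donor exclusions in section 6.1.2 cover living donors, split livers, positive serology, injury or abnormal anatomy, and "Donor livers with macrosteatosis of > 40% based on retrieval biopsy readout". None concerns donor age or DCD status.

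Section 10.2.1 removes from the Per Protocol population any subject "Ineligible for the study according to the donor organ inclusion and exclusion criteria", so donor eligibility feeds the primary analysis set. Section 10.3.4 lists "DCD (donation after circulatory death) patients" as a subgroup with no age qualifier. It lists donor age as a separate subgroup with no cut-point. Section 10.3.5 carries the same subgroups to the secondary endpoints. Section 10.3.4 adds: "No data imputation or statistical tests will be performed for these subgroup analyses". Sections 10.3 and 10.6 leave the detailed statistical analysis plan to be finalised before database lock.

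**The concern.** A stated age limit normally keeps someone out, and this one does not. The macrosteatosis limit makes the contrast plain: it appears as an inclusion item and again as an exclusion, so it binds. The 55-year limit appears only as part of one of four alternative routes into the trial, and donors above it enter by another route.

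Two things could be at stake. First, a site or programmer might take 55 as a ceiling for all DCD donors. Because donor ineligibility removes a subject from the Per Protocol population, that reading would alter the primary analysis set. Second, a reader of the DCD subgroup result might suppose that it describes donors of 55 or younger, when the subgroup definition admits older ones and asks for no count of them.

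**Working it through.** **1. The logic of the inclusion rule.** Inputs are the four items of section 6.1.1 and its any-one rule. Write A for age ≥ 40, C for cross-clamp ≥ 6 h, S for macrosteatosis above 0% and up to 40%, and D for DCD.

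Eligible on inclusion = A or C or (D and age ≤ 55) or S.

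A DCD donor with age > 55 has age ≥ 40, so A is true. Hence A or (D and age ≤ 55) is the same set as A or D. The DCD item still does work: it admits DCD donors under 40 with short cross-clamp time and no steatosis. Only its upper bound is redundant.

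**2. Enumeration.** Ages 0 to 100 (101 values) × DCD yes/no × cross-clamp yes/no × steatosis yes/no = 101 × 2 × 2 × 2 = 808 profiles.

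- Profiles whose eligibility changes when the bound is removed: 0.
- DCD profiles that fail inclusion at any age: 0.
- In whole years, any bound of 39 or more gives the same result.
- For contrast, a ceiling of 55 on all DCD donors would change 45 ages (56 to 100) × 2 × 2 = 180 profiles, all of them DCD donors over 55.

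A second grid, of DCD donors only, adds the macrosteatosis exclusion: ages 18 to 80 (63) × cross-clamp 4 h or 8 h × macrosteatosis 0%, 20% or 50% = 378 profiles. Eligible: 63 × 2 × 2 = 252, with the bound at 55 or removed. Over 55 there are 25 × 2 × 3 = 150 profiles. Of these, 25 × 2 × 2 = 100 are eligible, and the other 50 fail only on macrosteatosis. Profile counts are not patient frequencies.

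**3. Consistency.** The synopsis, section 4 and section 6.1.1 use the same any-one rule and the same 55-year wording. No passage applies 55 to all DCD donors. Section 10.2.1 refers back to these criteria and adds no age rule. The literal reading is therefore the only one the text supports.

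**4. Possible size.** The documents give neither the DCD share nor the share over 55. Assume DCD donors are 10% to 30% of 184, and 5% to 20% of those are over 55.

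- DCD subgroup: 184 × 0.10 = 18 to 184 × 0.30 = 55.
- Over 55: 184 × 0.10 × 0.05 = 0.9 to 184 × 0.30 × 0.20 = 11.0, so about 1 to 11 recipients.
- Effect on the DCD rate, if the event rate differs by 10 to 20 percentage points between the age groups: 0.05 × 10 = 0.5 points to 0.20 × 20 = 4 points.
- Sampling error of the DCD rate, assuming event rates of 10% to 30%: √(0.10 × 0.90 / 55) = 4.0 points to √(0.30 × 0.70 / 18) = 10.8 points.

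The largest assumed shift is about equal to the smallest of these standard errors.

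**The case for a change.** The strongest case for acting is that a number stated in the synopsis, the objectives and the inclusion criteria, yet doing nothing, invites misreading. Section 10.3.2 plans programmed checks of the inclusion and exclusion criteria, so someone must code this rule. A programmer who coded 55 as a DCD ceiling would drop subjects from the Per Protocol population whom the text keeps. A later analysis plan cannot settle how sites screen donors. One clarifying line and one extra table would cost little.

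Some of this stands. The bound is redundant, the DCD subgroup is not split at 55, and the donor-age subgroup does not fill that gap because it has no cut-point and is not crossed with DCD.

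The harm, however, requires someone to depart from an explicit rule. A check coded from section 6.1.1 as worded gives the right population. A miscoded one would show in the listing of individual major deviations that section 10.3.2 requires. It could not touch the mITT population, which takes all transplanted subjects regardless of eligibility (section 10.2.2).

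The case for splitting the endpoints at 55 is weaker still. No passage gives that age a role in the analysis, and the over-55 cell would be too small for a useful rate. Section 7.3 records donor age, and for DCD donors the time from withdrawal of support to cardiac standstill, so a count by age can be produced whenever it is wanted. The same four donor items appear for PROTECT in section 2.2, and section 1 describes this protocol as its continuation. Keeping them is therefore coherent, although PROTECT adds current standard acceptance criteria.

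**Conclusion.** The observation is correct, but it is a drafting redundancy and calls for no change. The 55-year bound alters eligibility for 0 of 808 profiles. The passages agree with one another and give each donor a determinate status. The primary analysis, the sample size and the descriptive status of the subgroups are untouched.

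The remaining effect is on how the DCD subgroup is described. It may include about 1 to 11 recipients of livers from donors over 55, and its rate may differ by 0.5 to 4 points from that for donors of 55 or younger. Both ranges rest on the assumed DCD share, over-55 share and rate difference; the documents do not say whether any such donor will be enrolled. An analyst who wants to show the age make-up of the subgroup can add a count from data already collected when the analysis plan is finalised. What the bound was meant to do clinically is for the sponsor and is not judged here.

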#### 6.1.2. Donor Exclusion Criteria

Donor livers will be excluded if they meet any of the following criteria:

- Living donors
- Liver intended for split transplants
- Positive serology (HIV, Hepatitis B surface antigen & Hepatitis C)
- Presence of moderate or severe traumatic liver injury, or anatomical liver abnormalities that would compromise ex- vivo preservation of the donor liver (i.e., accessory blood vessels or other abnormal anatomy that require surgical repair) and livers with active bleeding (e.g., hematomas)

- Donor livers with macrosteatosis of > 40% based on retrieval biopsy readout.

## 6.2. Recipient Eligibility Criteria

### 6.2.1. Recipient Inclusion Criteria

Recipients are required to meet all the following criteria on the day of transplant:

- Registered primary liver transplant candidate, male or female
- Age  $\geq$  18 years old
- Signed: (1) written informed consent document and (2) authorization to use and disclose protected health information.

### 6.2.2. Recipient Exclusion Criteria

Recipients will be excluded if they meet any of the following criteria on the day of transplant:

- Acute, fulminant liver failure
- Prior solid organ or bone marrow transplant
- Chronic use of hemodialysis or diagnosis of chronic renal failure, defined as chronic serum creatinine of  $> 3$  mg/dl for  $> 2$  weeks and/or requiring hemodialysis
- Multi-organ transplant
- Ventilator dependent
- Dependent on  $> 1$  IV inotropic support to maintain hemodynamics.

## 7. PRE-OPERATIVE TRIAL PROCEDURES

### 7.1. Subject Identification

All patients on the liver transplant waiting list who are being treated by trial investigators will be identified. Those patients who initially appear eligible for the trial will have the trial thoroughly explained to them, be invited to participate, and will be asked to sign an informed consent for participation in the trial prior to treatment. When a matching donor liver becomes available, the inclusion and exclusion criteria will be re-verified. When a final decision is made to transplant the liver, the recipient will be assigned a subject identification number.

### 7.2. Recipient Day of Transplant Assessment

The purpose is to conduct a final assessment of whether the potential consented recipient still meets the eligibility criteria. The following information will be verified and recorded on the day of transplant:

- **Eligibility:** Investigator will review and confirm that the potential consented recipient continues to meet all inclusion criteria and no exclusion criteria.
- **Demographics/Characteristics:**

- Date of birth or Age
- Gender, body mass index
- Race and Ethnicity
- Blood type and RH factor
- Recipient Model for End-stage Liver Disease (MELD) Score
- Recipient ID
- **Baseline Liver Function Tests:**
  - Bilirubin levels
  - Aspartate aminotransferase (AST)
  - Alanine aminotransferase (ALT)
  - Gamma-glutamyl transpeptidase (GGT)
  - Alkaline phosphatase
  - International normalized ratio (INR)
  - Serum Lactate level
- **Recipient Risk Factors & Medical History:**
  - Indication for transplantation: The primary etiology of Liver failure will be recorded
  - History of Hepatitis C
  - History of liver cancer
  - History of diabetes.

### 7.3. Donor Screening and Acceptance

The investigator or a member of her/his transplant team will evaluate the donor and the quality and suitability of the liver for transplantation and for enrollment in the trial. The following evaluations will be conducted and recorded:

- **Organ Donor Identification Number** (i.e., UNOS Donor ID)
- **Demographics:** Age, Date of birth (if available), gender, race, and ethnicity
- **Donor Characteristics:** Blood type & RH factor, body mass index
- **Donor's Cause of Death:**
  - Cause of death and date and time of pronouncement of brain death
  - If the donor is a DCD donor, total time in minutes from discontinuation of support to cardiac stand still
- **Medical History:**

- Active infection, positive serology for CMV, HIV, Hepatitis B or C, malignant tumors, and Liver disease
- History of diabetes (if available)
- **Donor Liver Assessment:** The donor Liver will be assessed prior to procurement and acceptance using the following methods:
  - **Liver Enzymes:** the following tests will be collected if available:
    - Bilirubin levels;
    - Aspartate aminotransferase (AST);
    - Alanine aminotransferase (ALT);
    - Gamma-glutamyl transpeptidase (GGT);
    - Alkaline phosphatase;
    - International normalized ratio (INR);
    - Lactate level.
  - **Liver Biopsy** (see [Appendix 1](#) of this document): A needle biopsy will be collected from all donor livers at time of retrieval at time of cross clamp in the donor. Only donor livers that are clinically suspected to be fatty by retrieval team visualization, will require a pre-retrieval biopsy readout to estimate the degree of macrosteatosis and confirm eligibility (> 0 and ≤ 40% macrosteatosis).
- **Eligibility:** The donor will be evaluated to document whether the eligibility criteria are met. Any other clinical reasons for not accepting donor liver at final assessment before retrieval will be recorded.

#### 7.4. Donor Liver Retrieval and OCS Preservation and Assessment

After final evaluation of the donor liver in donor's abdomen and upon acceptance into the trial, the investigators will retrieve and preserve the donor liver according to the following protocol:

- **Initial Liver Flush in Donor Body:** All donor livers will be flushed using cold Belzer UW® solution or Custodiol® HTK preservation solutions according to the institution's standard of care practice and the manufacturer instruction for use.
- **OCS Liver Back Table Flush:** All donor livers will be flushed on the back table using cold PlasmaLyte® solution supplemented with sodium bicarbonate (NHCO3) 10 mm/L, Epoprostenol Sodium 2 mics/L, and Methylprednisolone ~160 mg/L flush below, according to the following protocol:
  - **Hepatic Artery:** 1 liter flush at ~50-70 mmHg pressure bag
  - **Portal Vein:** 2 liters gravity drain
- **OCS Liver Perfusion:** The OCS Liver System will be primed using the following

OCS Liver Perfusate Composition	Recommended Dose
Packed Red Blood Cells (pRBCs)*	4-8 units
Albumin 25%	400 mls

OCS Liver Perfusate Composition	Recommended Dose
PlasmaLyte® solution	700-800 mls
Methylprednisolone	500 mgs
Dexamethasone	20 mgs
Sodium Bicarbonate (NaHCORR 3 RR) 8.4%	70 mmol
Adult Multivitamins for infusion e.g., INFUVITE®	1 unit
Calcium Gluconate 10% (100 mg/ml)	10 mls
Antimicrobials:	
Gram positive antibiotic e.g., Cefazolin	1 gm
Gram negative antibiotic e.g., Cirprofloxacin	100 mg
* type specific (or O negative blood group), , leukocyte reduced	

- OCS Liver Perfusion Additives:** In addition to the above OCS Liver perfusate, the following will be infused to the perfusate mix using an ex-vivo solution pump:

OCS Liver Perfusate Additives	
Continuous Infusion Mix	Dose
Total parenteral nutrition (TPN) Mix: CLINIMIX E TPN (4.25% Amino Acid / 10% Dextrose); PLUS Insulin 30 IU Glucose 25 gms Heparin 40,000 units	30 ml/hr
As Needed Additives	Dose
Prostacyclin infusion as needed to control Hepatic artery pressure e.g., Epoprostenol Sodium 0.5 mg	0-20 mics/hr
Bile Salts e.g., Taurocholic acid sodium (1 gm/50 ml)	3 ml/hr
NaHCORR 3 RR 8.4% to correct metabolic acidosis	1.5 meq/1 base excess

- Bile Salt Preparation:** All study sites will be provided sealed Gamma-sterilized vials of 1 gm of Taurocholic acid sodium in salt form to be mixed prior to retrieval according to the following steps:

- Add 50 ml of sterile water for injection using aseptic technique
  - Mix well to ensure all salt is dissolved.
- At the time of use the OCS operator will spike the stopper of the vial using a sterile OCS infusion line and connect to the OCS infusion delivery system.
- **The OCS Liver Preservation Parameters:** Donor livers will be perfused on the OCS Liver System with OCS parameters maintained within the following ranges
  - Hepatic Artery Pressure (mean HAP): 75-100 mmHg
  - Hepatic Artery Flow (HAF): 300-700 ml/min
  - Portal Vein Pressure (mean PVP): 4-8 mmHg
  - Portal Vein Flow (PVF): 700-1700 ml/min
  - Perfusion Temperature (Temp): 34°C
  - Oxygen gas flow 400-700 ml/min
  - Circulating arterial Lactate (Lact) trend: trending down over time.
- **Lactate and Liver Enzyme Levels During OCS Liver Perfusion Sampling Scheme:** The organ retrieval team will collect samples from the arterial port of the OCS perfusion circuit to measure lactate level using a standard blood analyzer according to the following protocol:
  - OCS Baseline arterial sample within the first 10-30 min of liver instrumentation.
    - Lactate
    - Liver enzymes: AST, ALT, GGT, total bilirubin, and ALP.
  - Lactate samples will continue to be collected from the device at approximately hourly intervals until lactate level is trending down, at this time, lactate samples should be done every 2 hours or after any active HAF or HAP adjustments.
  - OCS Final arterial sample before cooling liver on OCS
    - Lactate
    - Liver enzymes: AST, ALT, GGT, total bilirubin, and ALP.
- **Final Liver Cooling and Flush Arrest on OCS:** all donor livers on OCS will be cooled and flushed on the OCS using cold PlasmaLyte® solution supplemented with sodium bicarbonate (NHCO3) 10 mml/L, Epoprostenol Sodium 2 mics/L, and Methylprednisolone ~160 mg/L flush below, according to the following protocol:
  - **Hepatic Artery:** 1 liter flush at ~50-70 mmHg pressure bag
  - **Portal Vein:** 2 liters gravity drain.
- **Liver Biopsy (see Appendix 1):** a needle biopsy will be collected from donor livers preserved on OCS on the back table, post-preservation, immediately before re-implantation.

- **OCS Preservation Information:** the following information will be collected
  - Device Information (serial number, etc.)
  - Device Malfunction(s)
  - OCS system data collected by the device during the preservation run and uploaded into the EDC database.
- **Donor Retrieval Details:** The following information will be collected at time of Liver retrieval
  - Date and time of cross clamp of donor aorta.
- **OCS Details (Liver Instrumentation details):**
  - Total cold ischemia time between initial donor cross clamp and start of OCS Liver perfusion.
- **OCS Parameters and Enabled Measurements:** The following OCS Liver perfusion parameters and Liver metabolic conditions will be recorded:
  - HAP
  - HAF
  - PVP
  - PVF
  - Total Bile volume
  - OCS Liver arterial lactate level.

## 7.5. **Donor Liver Acceptance for Transplantation following OCS Liver Preservation**

All donor livers that are preserved on the OCS Liver System are expected to be transplanted into a matching consented recipient. Any decision to turn down livers after they have been retrieved and preserved on OCS Liver System should be done with notification to the Site PI and the donor liver examined by the transplant center's qualified liver transplant pathologist and/or tissue slides/samples to be sent to core lab for the study for further examination. All reasons for turning down a donor liver after it has been preserved on the OCS Liver System will be collected in the eCRFs.

